Table 2	Association between Tamsulosin and	35
	Silodosin with side effects	

LIST OF FIGURES

Serial No.	Figure	Page No
Figure 1:	Pie chart of patients using Silodosin and Tamsulosin (Medicine Advised)	33
Figure 2	Bar Chart showing comparison of stone expulsion rate in Tamsulosin and Silodosin groups	43
Figure 3	Survival function	41

L	

LIST OF ABBREVIATIONS

AUA	American Urology Association
EAU	European Association of Urology
MET	Medical expulsive therapy
PNL	Percutaneous Nephrolithotomy
RCTs	Randomized controlled clinical trials
SPSS	Statistical Package for the Social Sciences
α-AR	Alpha adrenergic receptor
LUTS	Lower Urinary Tract Symptoms

SWL	Shock wave lithotripsy
ESWL	Extracorporeal Shock Wave Lithotripsy
CKD	Chronic kidney disease
SET	Stone ejection time
USD	Ureteric stone disease
SER	Stone ejection rate

Abstract

Introduction: Ureteric stones is a very common disease world over. Medical Expulsive therapy (MET) for stones is a recognized treatment option practiced. Tamsulosin is used commonly in our population for MET however Silodosin another highly uroselective newer drug, with lesser side effects, is not used frequently for this purpose and is still under research. Both of these drugs lead to relaxation of lower ureteric smooth muscle hence facilitate in stone removal.

The rationale of this study is to compare the efficacy of Tamsulosin and Silodosin in MET (medical expulsive therapy) with regards to stone expulsion rate as well as to compare the side effect profile in our population.

Methodology: This is a prospective randomized control trial in Outpatient department of Sir Ganga Ram hospital, Lahore, on 208 patients with ureteric stone who fulfil the inclusion criterion, divided randomly into two groups with 104 patients in the Tamsulosin group and 104 patients in Silodosin group (1:1 ratio). However, 16 patients were subsequently excluded on account of premature end of study, and 12 due to being lost to follow-up (Figure 1). Out of remaining 180 patients 89 were of Tamsulosin and 93 were in Silodosin group. Demographic data including patients' age and comorbid, stone-related data including size, location, laterality and number of stones and duration of symptoms were recorded. The patients were called for follow up at 4 weeks

with an X-ray KUB without bowel preparation. We noted if the stone had passed or not.

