It is hypothesized that efficacy and safety of medical expulsive therapy, containing tamsulosin and silodosin, is almost the same and silodosin can be used with the same efficacy for the treatment of lower urinary tract calculi.

Alternative Hypothesis:

Silodosin is better than Tamsulosin in efficacy and safety.

OPERATIONAL DEFINITIONS:

STONE CLEARANCE:

Stone clearance will be defined as no evidence of stone on follow up X-ray KUB imaging at 4 weeks .

ANCILLARY PROCEDURES:

Additional urological procedures needed to remove the same stone for which medical expulsive therapy was given if it fails to remove the stone completely.

SIDE EFFECTS:

Any undesirable effect noticed after prescription of the drug including but not limited to abnormal ejaculation, headache, orthostatic hypotension, backache and gastritis etc.

MATERIALS AND METHODS:

STUDY DESIGN:

Prospective randomized control trial.

STUDY SETTING:

Outpatient department of Sir Ganga Ram hospital, Lahore.

DURATION OF STUDY:

18 months.

DURATION OF TREATMENT:

Four weeks.

SAMPLE SIZE:

Using the open-epic software, the sample size was estimated. The minimum sample size that we require is 208 patients with ureteric stone who fulfil the inclusion criterion with 104 in one group receiving tamsulosin and 104 in silodosin group (1:1 ratio) with an inflation of 10 percent for estimated loss to follow up, with an anticipated expulsion rate ranging from 58-64 percent in tamsulosin group and 78-83 percent in silodosin group with a risk difference of 19 to achieve a power of 80 percent and a level of significance of 5 percent.

SAMPLING TECHNIQUE:

Patients visiting the outpatient department of Sir Ganga Ram hospital will be selected by simple random sampling, fulfilling the inclusion criteria.

SAMPLE SELECTION:

Adult male and female patients fulfilling the inclusion criteria will be assigned into two groups by random allotment, 1^{st} group will be given Tamsulosin and 2^{nd} group will be given Silodosin for four weeks.

INCLUSION CRITERIA:

Following factors make up the inclusion criteria for this study.

- Patients between ages 18 years 55 years.
- Solitary unilateral ureteral stone
- Stone sizes less than 10 mm measured on non-contrast computed tomography of kidney, ureter and bladder.
- Stones being treated primarily with medical expulsive therapy
- Radio opaque Stone

EXCLUSION CRITERIA:

The presence of following factors will exclude the patients from our study:

- Pregnancy
- Untreated UTI

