Data will be entered and analyzed on SPSS version 22. Percentages and frequencies will be calculated for the demographic variables of the patients. The comparison of the two groups will be made by using T- test. P-value of less than 0.05 will be considered significant and the power used will be 0.80.

RESULTS

Frequency and percentage of demographic data

Variables		Frequency	Percentage	
Gender	Male	105	58.7	
	Female	74	41.3	
Income	Less than	108	60.3	
status	50000			
	50000 -150000	69	38.5	
	Greater than	2	1.1	
	150000			
	Normal	166	92.7	
BMI	Obese	13	7.3	
	None	136	76.0	
Comorbidity	HTN	33	18.4	
	Diabetes	10	5.6	

This information sheds light on the sample population's health and demographic distribution, showing a preponderance of people with normal BMIs and lower income levels, as well as a significant percentage of people without comorbid diseases.

In our study there are total 179 patients out of which 74 are females (41.3%) and 105 males (58.7%).

The income, 108 people, or 60.3% of the total, make less than 50,000Rs in month. Just 2 members, or 1.1 percent, make more than 150,000 monthly, while 69 participants (38.5%) have monthly salaries between 50,000 and 150,000.

13 persons (7.3%) are classed as obese, while 166 people (92.7%) have a normal BMI. These numbers represent a sizable fraction of the sample. In terms of comorbidities, 136 individuals (76.0%) state they have no comorbid conditions. Of the people with comorbidities, 10 (5.6%) had diabetes, and 33 (18.4%) had hypertension (HTN).

[figure not shown]

Figure 1: Pie chart of patients using Silodosin and Tamsulosin (Medicine Advised)

Use of medicine (Figure 1)

Tamsulosin and Silodosin, the two drugs prescribed to a group of patients, are distributed as shown in the pie chart. Of the patients, 43% were advised to take Tamsulosin, which is shown as the blue section on the chart. And (57%) of the patients were advised to take silodosin, as shown by the red segment.

Table2: Patient demographic characteristics and study variables are

Varibales	Tamsulosin	Silodosin	p-value	
Body Mass index	Normal	72(43.4%)	94(56.6%)	0.730
	obese	5 (38.5%)	08(61.5%)	
Laterality	Right	65(55.6%)	52(44.4%)	0.001
	Left	12(19.4%)	50(80.6%)	
Symp To CT	Less than 1 week	67(64.4%)	37(35.6%)	
	More than 1 week	10(15.2%)	56(84.8%)	0.001
	More than 2 week	0 (0.0%)	09(100%)	
Posl n Ureler	Proximal	28(51.9%)	26(48.1%)	

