	Mid	08(17.4%)	38(82.6%)	0.001
	Distal	41(51.9%)	38(48.1%)	
Water intake	Less than 1 litre	59(54.6%)	49(45.4%)	
	More than 1 litre	18(25.4%)	53(74.6%)	0.001
Analgesic requirement	Yes	26(61.9%)	16(38.1%)	0.005
	No	51(37.2%)	86(62.8%)	
Time for removal	Less than 14 days	6(10.3%)	52(89.7%)	
	14-21	14(27.5%)	37(72.5%)	0.001
	22-28	57(81.4%)	13(18.6%)	

presented as frequency and percentage with association

The table compares several factors along with the corresponding p-values to assess statistical significance between two drugs tamsulosin and silodosin.

First, based on Body Mass Index (BMI), 43.4% of those with a normal BMI were prescribed Tamsulosin, while 56.6% were recommended Silodosin. On the other hand, among those who were obese, 38.5% were given Tamsulosin and 61.5% were given Silodosin; p-value came out to be 0.730, which meant that there was no statistically significant variation in the medication preferences according to BMI.

15.2% of patients who had pain for more than a week prior to CT scan, received Tamsulosin while 84.8% received silodosin.

51.9% of the patients with proximal ureteric stone were given Tamsulosin and 48.1% received Silodosin.

82.6 percent of patients with mid-ureteric stone problems received Silodosin, while 17.4% received Tamsulosin.

51.9% of patients with distal ureteric stones received Tamsulosin and 48.1% on Silodosin.

Only 38.1% of patients on Silodosin required analgesics, whereas 61.9% of patients on Tamsulosin used analgesics.

89.7% of patients on silodosin had their stone removed in less than 14 days, while only 10.3% of the patients on Tamsulosin had their stone removed in aforementioned duration.

72.5% of patients on Silodosin had their stone removed in 14-21 days, while only 27.5% of the patients on Tamsulosin had their stone removed in same duration.

Moreover, 81.4% on Tamsulosin had their stone removed in 22-28 days and 18.6% patients on Silodosin had it removed in same duration.

		Tamsulosin	Silodosin	p- value
Side	None	61 (40.1%)	91(59.9%)	
effect	Othostatic	09 (60.0%)	06(40.0%)	
	hypotension			0.3.15
	Abnormal	2(66.7%)	1(33.3%)	
	ejaculation			
	Headache	5(55.6%)	4 (44.4%)	

Table 2 Association between Tamsulosin and Silodosin with side effects

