This bar chart presents a comparative examination of the rates of stone expulsion for patients who were suggested to take Tamsulosin or Silodosin during three distinct time periods—less than 14 days, 14–21 days, and 21–28 days.

The results are color-coded, with red bars denoting silodosin and blue bars denoting tamsulosin.

Silodosin shows a markedly greater efficacy in stone expulsion, with about 55 patients expulsing stone in less than 14 days in comparison to just about 5 patients on Tamsulosin.

This suggests that Silodosin is far more successful at facilitating stone removal in less time than Tamsulosin.

While in 14–21days duration, Silodosin continues to work better than Tamsulosin in removing stones. About 20 patients on Tamsulosin were able to successfully remove stone, compared to about 30 people on Silodosin. This implies that while tamsulosin is also beneficial, silodosin retains greater efficacy.

In the span of 21–28 days, 57 patients on Tamsulosin while 13 on Silodosin were able to eliminate stones. In general, Silodosin is quite successful for rapid stone ejection during the first two weeks. Using the intended period for stone

ejection to guide medicine selection, this time-dependent efficacy analysis offers clinicians important information.

[figure not shown]

Figure 3 Survival function

This statistical method is commonly used to estimate the time until an event occurs and to compare the survival curves of different groups. In this case, Kaplan–Meier analysis was performed to assess the duration that patients required to expel kidney stones while receiving either silodosin or tamsulosin treatment. The rate of the expulsion of stone and the time for it, for both groups, was evaluated using this method, as can be seen in Figure 2.

The log-rank test was applied to compare the rate and time for stone expulsion between the two groups. It is a hypothesis test for comparing the survival distributions of two samples. It was used in this study to see if patients treated with silodosin and those treated with tamsulosin had significantly different times for stones to be expelled. With a p-value of 0.05, the log-rank test findings showed that there was statistically significant difference between the two groups. This indicates that both groups' times to stone expulsion were statistically comparable.

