Similar results were seen in another study showing that, individuals receiving just tamsulosin treatment needed a greater average analgesic dosage of 391.43 \pm 165.60 mg with a p-value of 0.005, which denotes substantial significance, the necessary(50).

Similarly, a study showed statistically significant difference in the amount of analgesics needed by patients treated with Silodosin compared to those treated with tamsulosin only. The robustness of the conclusion was highlighted by the fact that the group receiving Silodosin treatment required considerably fewer analgesics than the groups receiving Tamsulosin, with a p-value of < 0.001(51).

Conclusion

An effective treatment for ureteral stones is medical expulsive therapy. According to our findings, silodosin has a safer profile and is more successful than tamsulosin at ejecting ureteric stones.

Silodosin had an increased rate of stone expulsion and took less time in stone expulsion compared to those treated with Tamsulosin.

In addition, patients treated with silodosin reported fewer side effects, such as a retrograde ejaculation, orthostatic hypotension and headaches as compared to those taking Tamsulosin.

In addition, those who received Silodosin needed less analgesic medication than those who received Tamsulosin.

•

REFERENCES

- Ahmed AFAM, Al-Sayed AYS. Tamsulosin versus Alfuzosin in the Treatment of Patients with Distal Ureteral Stones: Prospective, Randomized, Comparative Study. Korean J Urol. 2010 Mar;51(3):193–7.
- 5. Pietropaolo A, Proietti S, Geraghty R, Skolarikos A, Papatsoris A, Liatsikos E, et al. Trends of 'urolithiasis: interventions, simulation, and

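### The arm sizes contradict one another (104/104 randomised, 89/93 retained, 77/102 tabled), so the by-arm results cannot be verified as a randomised comparison

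*Combined protocol and SAP*

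**What the plan says.** - **Planned and randomised.** The Sample Size section sets "104 in one group receiving tamsulosin and 104 in silodosin group (1:1 ratio"), and the Abstract says 208 patients were divided that way.
- **Exclusions.** The Abstract removes 16 patients because the study ended prematurely and 12 lost to follow-up. It does not split either number by arm. It cites Figure 1 at this point, but the list of figures and the caption both show Figure 1 to be a pie chart of the medicine advised.
- **Retained.** "Out of remaining 180 patients 89 were of Tamsulosin and 93 were in Silodosin group".
- **Results total.** "In our study there are total 179 patients out of which 74 are females (41.3%) and 105 males (58.7"%).
- **Results split.** The Figure 1 text puts 43% on tamsulosin. "And (57%) of the patients were advised to take silodosin, as shown by the red segment".
- **Time for removal.** The text on the last of the three time bands reads: "Moreover, 81.4% on Tamsulosin had their stone removed in 22-28 days and 18.6% patients on Silodosin had it removed in same duration". The table has no row for stones not removed.
- **Analysis.** The Data Analysis Procedure says "The comparison of the two groups will be made by using T- test". It names no analysis set and no rule for missing outcomes.
- **Conclusion.** "Silodosin had an increased rate of stone expulsion and took less time in stone expulsion compared to those treated with Tamsulosin".

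**The concern.** Numbers in an arm can only fall between randomisation and analysis. Here one arm rises between the Abstract and the tables, and three different totals are given for the patients who remain (180, 182, 179). The possible explanations have very different consequences. If the Abstract split is simply wrong, the tables hide very unequal loss between the arms. If the Abstract split is right, some patients are tabled under a drug they were not allocated to, and the by-arm comparisons are no longer those created by randomisation.

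The main outcome is also exposed. Stone clearance is defined at 4 weeks, yet the removal-time table contains no failures in either arm. Read as it stands, it shows complete clearance in both, so any difference at 4 weeks would have to come from the patients who are not in the table.

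**Working it through.** **1. The plan's own total.** 208 − 16 − 12 = 180, which reproduces the stated total. The split given for it does not: 89 + 93 = 182.

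**2. Column sums of every by-arm variable in the Results tables.**

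| Variable | Tamsulosin | Silodosin |
|---|---|---|
| Body mass index | 72+5 = 77 | 94+8 = 102 |
| Laterality | 65+12 = 77 | 52+50 = 102 |
| Symptom-to-CT time | 67+10+0 = 77 | 37+56+9 = 102 |
| Position in ureter | 28+8+41 = 77 | 26+38+38 = 102 |
| Water intake | 59+18 = 77 | 49+53 = 102 |
| Analgesic requirement | 26+51 = 77 | 16+86 = 102 |
| Time for removal | 6+14+57 = 77 | 52+37+13 = 102 |
| Side effects | 61+9+2+5 = 77 | 91+6+1+4 = 102 |

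77 + 102 = 179. The shares 77/179 = 43.0% and 102/179 = 57.0% match the Figure 1 text; the Abstract's split would give 89/182 = 48.9% on tamsulosin.

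**3. Can one slip explain it?** From 89/93 to 77/102, tamsulosin loses 12 and silodosin gains 9. Changing one Abstract number to restore 180 (87/93 or 89/91) still leaves silodosin below 102.

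**4. Implied losses from 104 per arm (Fisher exact test).**

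- Under 89/93: 104 − 89 = 15 (14.4%) v 104 − 93 = 11 (10.6%), total 26, p = 0.53.
- Under 77/102: 104 − 77 = 27 (26.0%) v 104 − 102 = 2 (1.9%), total 29, p = 3 × 10⁻⁷.

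Neither total equals the stated 16 + 12 = 28.

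The 77/102 split alone is only weak evidence against 1:1 allocation (binomial test against one half, p = 0.07). The difficulty is its conflict with 93 retained, or, if 93 is wrong, the very unequal loss.

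**5. Effect on 4-week clearance.** This assumes that 77 and 102 are subsets of the 104 allocated to each arm and that every tabled patient cleared. Differences are silodosin minus tamsulosin.

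| Patients not tabled | Silodosin | Tamsulosin | Difference |
|---|---|---|---|
| Tamsulosin cleared, silodosin not | 102/104 | 104/104 | −1.9 points |
| Not cleared in either arm | 102/104 (98.1%) | 77/104 (74.0%) | +24.0 points |
| Silodosin cleared, tamsulosin not | 104/104 | 77/104 | +26.0 points |

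**6. Effect on expulsion before 14 days.** The table gives 6 (tamsulosin) v 52 (silodosin). Under the same subset assumption, count all 27 missing tamsulosin patients as early and neither missing silodosin patient as early: (6+27)/104 = 33/104 (31.7%) v 52/104 (50.0%), p = 0.011.

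Suppose instead that 93 is right and 9 early expellers tabled under silodosin belong to tamsulosin. The tabled arms become 86 and 93, with 15 and 43 early. With the same extreme treatment of the missing (18 tamsulosin early, 11 silodosin not), the result is 33/104 (31.7%) v 43/104 (41.3%), p = 0.19. The direction holds; significance does not.

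**7. A variable fixed before randomisation.** Symptom-to-CT time under 1 week is 67/77 v 37/102. Suppose all 27 missing tamsulosin patients were at 1 week or more and both missing silodosin patients under 1 week. The split would still be 67/104 v 39/104, p = 0.0002. If the subset assumption holds, loss alone is therefore an unlikely explanation. Chi-square tests on the tabled rows also show imbalance in laterality (p = 3 × 10⁻⁶), symptom-to-CT time (p = 6 × 10⁻¹¹) and stone position (p = 0.0003).

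**The case against.** The strongest reply accepts the arithmetic but disputes what is built on it.

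- **The bounds assume what is in doubt.** They take the tabled arms as subsets of the allocated arms, while the concern allows that patients may be grouped wrongly. This stands as a limit: the 4-week range and p = 0.011 are conditional, and step 6 shows the latter does not survive one plausible regrouping.
- **No 4-week clearance proportion is reported, and the table may hold only patients who passed a stone.** The documents do not say this, and the Results call 179 the study total while the removal-time rows use up all 179. Complete clearance is the natural reading. If the table is restricted to successes, 4-week clearance is unknown, which supports the Conclusion no better.
- **Some flow is given.** True: exclusions are listed by reason and retained numbers by arm. The split of the 28 by arm and the step from 180 to 179 are missing. The missing figure images do not explain this, since none of the three listed figures is a flow diagram.
- **The Figure 2 text is approximate.** It says "About 20 patients on Tamsulosin were able to successfully remove stone, compared to about 30 people on Silodosin" for the middle band, and its counts add to roughly 5+20+57 = 82 v 55+30+13 = 98. These are rounded readings, and nothing here depends on them.
- **The Kaplan-Meier number at risk may be in the figure not shown.** That is possible; the text does not give it.
- **No randomisation list is described.** Correct: the text mentions only random allotment, so the cost of checking is partly an assumption.

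**Conclusion.** The concern holds, and the counts are wrong as written. The three totals disagree, and 93 silodosin patients retained cannot become 102 tabled through loss. The documents do not show which figure is in error, so no by-arm result, on efficacy or safety, can at present be verified as a comparison of randomised groups. This does not show that randomisation failed; the baseline imbalances make the check urgent without settling its outcome.

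The 4-week difference could lie between −1.9 and +26.0 points if the tabled patients are subsets of their allocated arms and all of them cleared. On that footing the Conclusion's higher expulsion rate is not supported at 4 weeks. The advantage before 14 days is less fragile: its direction survived both extreme cases tried, but its significance survived only one. This must be fixed before the by-arm results are relied on.

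**What to change.** 1. Check the tabled arm of every patient against the randomisation list or other allocation record. Correct 180/182/179 and 89/93 v 77/102. If no such record survives, say so.
2. Report flow by arm (randomised, excluded with reason, lost, analysed), and explain what the 16 exclusions for the study ending early were.
3. State the analysis set: for the main analysis, all 208 patients in the arm to which they were allocated.
4. Add a row for stones not removed by 4 weeks, and give the numbers at risk by arm for the Kaplan-Meier analysis.
5. Show the 4-week result under several missing-outcome assumptions: missing as not cleared, multiple imputation, and best and worst cases. If the 16 exclusions were administrative, censor those patients in the time-to-expulsion analysis. Rely on no single assumption.
6. Qualify the Conclusion on expulsion rate until this is done.

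The cost is a check of records, assuming allocation was recorded, plus a flow table, a statement of the analysis set and a re-run. No new patients are needed. Tamsulosin clearance could fall from the 100% the table implies to as low as 74.0% if missing counts as not cleared and every tabled patient cleared. The 4-week comparison may become inconclusive.

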The data showed that patients treated with silodosin demonstrated a higher rate of stone expulsion and faster stone expulsion compared to those treated with Tamsulosin. Though the difference did not achieve statistical significance in this trial, it shows that silodosin may be more beneficial in aiding kidney stone removal. The evaluation of rate and time of stone expulsion for both groups was conducted using Kaplan–Meier analysis, as depicted in Figure 2. This statistical method is commonly used to estimate the time until an event occurs and to compare the survival curves of different groups. In this context, the Kaplan–Meier analysis was utilized to assess the duration it took for patients to expel kidney stones while being treated with either silodosin or tamsulosin.

DISCUSSION

After prostate pathology and urinary tract infections, renal stones are the third most frequent urinary tract disorder. Ureteral stones account for 14% of stones in the urinary system, most of which are in the distal ureter. Five to ten percent of people have urolithiasis. Their rising incidence is a serious cause for concern(35).

Stones can be treated medically or surgically according to European and American urology associations. The medical management (MET) has its own advantages and is preferred over surgical approach as it is has less risks involved than the surgical procedures. For (MET) medical expulsive therapy we need to keep in view various parameters including the stone's size, position, and ureteric characteristics. The medical care of ureteral calculi has significantly improved since the market saw the release of efficient medicinal therapeutic agents. The results of multiple investigations suggest that alpha blockers aid in the transit of ureteral stones. These have shown that this strategy may speed up and ease the ureteral stones' natural passage. α -AR blockers have been suggested by recent worldwide standard guidelines as a treatment for ureteral stones in adults and adolescents.

In 1970, it was initially reported on how adrenergic receptors function in the human ureter. Alph adrenergic receptor agonists preserve ureteral peristalsis, which may aid in a spontaneous stone passage, while also preventing the uncoordinated muscular activity associated with renal colic. Instead of totally stopping the action of the ureteric smooth muscle, alpha blockers primarily cause relaxation of the human ureter's distal portion.

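### The null hypothesis asserts similarity with no margin in a superiority-sized trial, so not rejecting it proves nothing; separately, the report reads one log-rank test in incompatible ways

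*Combined protocol and SAP*

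**What the plan says.** **Hypotheses.** The Null Hypothesis states that efficacy and safety of expulsive therapy with the two drugs "is almost the same and silodosin can be used with the same efficacy for the treatment of lower urinary tract calculi". The Alternative Hypothesis is "Silodosin is better than Tamsulosin in efficacy and safety".

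**Design.** The Sample Size section uses an "anticipated expulsion rate ranging from 58-64 percent in tamsulosin group" and "78-83 percent in silodosin group with a risk difference of 19", with 80% power, a 5% level, 1:1 allocation and a 10% allowance for loss to follow-up, giving 104 per group. Sidedness is not stated. No equivalence or non-inferiority margin appears anywhere. Clearance is defined on X-ray KUB at 4 weeks. The Data Analysis Procedure treats a p-value below 0.05 as significant and does not say what may be concluded otherwise.

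**Results.** Under Figure 3, a log-rank p of 0.05 is reported and called significant. The next sentence says that the two groups' "times to stone expulsion were statistically comparable". The following paragraph opens a sentence with "Though the difference did not achieve statistical significance in this trial" and goes on to suggest that silodosin may be more helpful. The Conclusion says silodosin is more effective and safer.

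**The concern.** A null hypothesis for a superiority test should state no difference. This one states an unquantified similarity ("is almost the same") and attaches a conclusion about use. Read literally, retaining it after a non-significant test would license the statement that silodosin works equally well. A trial sized to detect 19 points controls the risk of a false claim of difference. It does not control the risk of a false claim of sameness, because nothing defines how close is close enough.

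The second issue is what the report made of its main time-to-event comparison. If one test is described as significant, comparable and non-significant, a reader cannot tell what was found or how it supports the conclusion of superiority.

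**Working it through.** **1. The plan's own sample size.** Inputs from the Sample Size section: 59% v 78% (a pair inside the stated ranges, 19 points apart), two-sided 5%, 80% power. With mean proportion 0.685:

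n = [1.96·√(2·0.685·0.315) + 0.8416·√(0.59·0.41 + 0.78·0.22)]² / 0.19² = (1.2876 + 0.5412)² / 0.0361 = 92.6, so 93 per arm.

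93/0.9 = 103.3, so 104 per arm and **208 in total**, as stated. The pair 64% v 83% with continuity correction gives 94 per arm; 94 × 1.1 = 103.4, again 104. One-sided versions at a 19- to 20-point difference give totals of 146 to 188. The design is thus a two-sided superiority calculation.

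**2. What non-significance could show.** Evaluable patients: 104 × 0.9 ≈ 94 per arm. The 95% half-width is 1.96·√(p₁q₁/n₁ + p₂q₂/n₂). The groups analysed in the Results were 77 and 102.

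| Clearance rates | 94 v 94 | 77 v 102 |
|---|---|---|
| 61% v 80% | 12.8 points | 13.4 points |
| 70% v 70% | 13.1 points | 13.6 points |
| 61% v 61% | 13.9 points | 14.4 points |

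**3. Chance of missing a real deficit.** Assume 70% on tamsulosin and 60% on silodosin, 94 per arm.

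- Standard error under the null: √(2·0.65·0.35/94) = 0.0696.
- Standard error under the alternative: √((0.70·0.30 + 0.60·0.40)/94) = 0.0692.
- P(non-significant) ≈ Φ((1.96·0.0696 − 0.10)/0.0692) = Φ(0.53) ≈ **0.70**.

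**4. If equivalence had been intended.** The margins here are assumptions, since none is given. Two one-sided tests at 5%, 80% power, 61% in both arms: n = 2·0.61·0.39·(1.645 + 1.282)²/margin².

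| Assumed margin | Per arm | Total after /0.9 | Power with 94 per arm |
|---|---|---|---|
| 10 points | 408 | 908 | about 0% |
| 15 points | 182 | 406 | about 36% |
| 19 points | 113 | 252 | about 70% |

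**5. The log-rank result against the report's own counts.** The removal-time rows of the Results table of patient characteristics and study variables:

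| Interval | At risk (tam / silo) | Removed (tam / silo) | Expected, silo | Variance |
|---|---|---|---|---|
| <14 days | 77 / 102 | 6 / 52 | 33.05 | 9.66 |
| 14–21 days | 71 / 50 | 14 / 37 | 21.07 | 7.21 |
| 22–28 days | 57 / 13 | 57 / 13 | 13.00 | 0 |
| Sum | | 77 / 102 | 67.12 | 16.88 |

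Chi-square = (102 − 67.12)²/16.88 ≈ **72.1**, 1 df, p about 2 × 10⁻¹⁷. A plain 3×2 chi-square gives 72.4, p about 2 × 10⁻¹⁶. The same table prints p = 0.001 for this row. Neither a log-rank p of 0.05 nor comparability fits these counts.

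**6. The printed p-value against the plan's rule.** The plan requires p below 0.05. A p of 0.05 as printed does not meet that; the unrounded value is not given.

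**The case against.** **The report does not consistently treat non-significance as equivalence.** A reader might infer that the null's wording led the authors to turn a non-significant test into proof of sameness. The documents do not support that. The sentence about comparability directly follows one calling the same result significant, so it is a self-contradiction. The next paragraph, which does call the result non-significant, leans towards silodosin. The side-effect text treats p = 0.315 as calling for larger samples, and the Conclusion claims superiority. This objection stands: the link from the null's wording to the results is conjecture.

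**The plan never says that a non-significant result will be reported as equal efficacy.** True. Its only rule concerns p below 0.05, and the null can be read as a clumsy statement of no difference. The point is therefore about what the wording would permit, which a few words can close off.

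**A directional alternative beside a two-sided test is common.** Also fair. Restating the alternative is mostly tidying, though sidedness is left unstated and should be fixed.

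**The 13-point interval concerns 4-week clearance, while the comparability sentence concerns time to expulsion.** Correct. Steps 2 to 4 bear on the hypothesis and step 5 on the results; neither is evidence for the other. The rates of 70% v 70% and 70% v 60% are illustrations, not planned or observed values.

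**Conclusion.** Two things hold, and they are separate.

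First, the null hypothesis is mis-stated for this design. With no margin and about 94 evaluable per arm, a non-significant result leaves differences of about 13 points open (13.4 to 14.4 with 77 v 102), and a true 10-point deficit would go undetected about 70% of the time. Retaining the null cannot support equal efficacy. These figures assume clearance of roughly 60% to 80% and the planned 10% loss.

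Second, the report's statements about one log-rank test are incompatible with each other, and the printed p does not fit the tabulated times. The recalculation uses three grouped intervals and is a consistency check, not an estimate of treatment effect. A reader might take its tiny p-value as proof that silodosin is superior. That would go too far: the table gives every patient in both arms (77/77 and 102/102) a removal time by day 28, so those who did not pass the stone may have been left out.

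The point deserves correction because it touches the trial's main question. It does not change the sample size, and it does not show that an equivalence conclusion was the one finally drawn.

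**What to change.** **In the plan.** State the null as equal 4-week clearance proportions and the alternative as a difference, tested two-sided at 5%. Delete the clause on using silodosin with equal efficacy. Add that a non-significant result is inconclusive, that the risk difference will be reported with a 95% confidence interval, and that no equivalence claim will be made. If equivalence or non-inferiority is wanted, it needs a pre-specified margin and its own sample size.

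**In the results.** Remove the comparability statement, but not that alone: the significant and non-significant readings would still conflict. Re-run the log-rank test on individual times, censoring patients who did not expel the stone. Report the exact p-value, and reconcile the Figure 3 text, the paragraph after it and the Conclusion with that result and with the removal-time table.

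**Cost.** A few sentences in the plan, one re-analysis of existing data, and edits to the results text and Conclusion. The sample size stays at 208.
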